- Unanticipated problems that do not fit the definition of an adverse event, but which may, in the opinion of the investigator, involve risk to the subject, affect others in the study, or significantly impact the integrity of study data. An example of this might be a report of accidental destruction of a study record;
- Unplanned protocol deviations/violations that have already occurred, that may adversely affect the rights, safety or welfare of subjects or the integrity of the study data, AND for which IRB approval was not obtained.

In reporting any deviations or adverse events to the IRB, the PI will submit a report to the IRB of record in eIRB via a Further Study Action for Protocol Event Report.

In addition to reports issued to the IRB, any unanticipated problem involving risks to subjects or others or any serious or continuing noncompliance with 45 CFR 46 or IRB requirements must be reported to the sponsoring agency (NIH) and to the Office for Human Research Protections (OHRP), HHS, per NIH policy.

5.a Medical Monitoring

i Investigator only

N/A. This is a non-significant risk study and interested candidates will not be undergoing medical procedures as part of this study.

5.b Definitions of Adverse Events

An adverse event is any undesirable experience associated with the use of a medical product in a patient. Adverse events may occur during the course of this study. The medical device that will be used in these studies is the FDA HDE approved Argus II Retinal Prosthesis System.

5.c Classification of Events

See Section E5.

5.d Data Collection Procedures for Adverse Events

See Section E5.

5.e Reporting Procedures

See Section E5.

5.f Adverse Event Reporting Period

See Section E5.

5.g Post-study Adverse Event

This is a non-significant risk study, no post-study adverse events are anticipated.

E6 Study Outcome Measurements and Ascertainment

Our study will determine whether the following hypotheses are correct:

1. The augmented systems expand users' ability to identify targets in the field of view and to usefully interpret the egocentric information obtained from the retinal prosthesis by augmenting the basic Argus II device with the capability of decluttering the scene and by providing discriminative information to convey object identities and locations.
2. Aided by the augmented system, the retinal prosthesis is capable of enabling the formation of an externalized spatial image that aids navigation.

These hypotheses will be tested statistically with sighted subjects (see Section F) by measuring proportion correct assessments as well as through bias and precision measurements. Argus II subjects will be assessed individually to determine whether augmentation leads to lower error, and their error will be quantified through comparisons with the sighted subjects.

F Statistical Plan

F1 Sample Size Determination and Power

No significance testing will be possible with Argus II participants due to the small number of people expected to be recruited for each Argus II participant group in this study (approximately 5).

Importantly, however, we will use the sighted subjects, who simulate the performance of Argus II users through the head mounted display conveying information similar to what is perceived by Argus II users, as a baseline. As described in G3, we characterize performance by Argus II users on any given task relative to this baseline.

In particular, for tests with sighted subjects, we use within-subject factorial designs and test with conventional ANOVA statistics; inter-subject correlations between abilities tests can also be computed. We use sample sizes based on prospective power analysis. A sample size of 20-30 subjects was calculated with [9] to achieve

a power greater than 0.80 at the 0.05 level of significance, using effect sizes from previous studies reporting perceived spatial layout in within-subject designs [10]. As a more general point, the experiments use a within-subject design, in which every subject provides a replicate of the entire study. In psychophysical research (i.e., where a physical variable is parametrically explored), these designs are typically done with populations on the order of 10-20 participants. The proposed sample is also consistent with similar studies of navigation by spatial updating (e.g., [11]).

F2 Analysis Plan

For each measure, the Argus II participants will be characterized by the z-score distance of their performance from the sighted participants (as computed with their mean and variance). We will use two other approaches to assess the Argus II participants' performance: (i) Use standards from the literature for basic psychophysical effects, including setting .2 as an effective d' score for 2- choice discrimination, based on Cohen's d effect-size statistics; setting 25% as the expectation for a size difference threshold, and setting a standard of 15° for absolute pointing error based on screening cutoffs in previous work. (ii) Set standards by considering the device capabilities; in particular, use distance expressed in device pixels between target and pointing locations in order to measure localization error. Finally, we intend to test the effects of learning by assessing performance over time. For this, we will fit trends to the measures over repeated trials and assess the linear component for a positive slope.

F3 Statistical Methods

See previous sections for additional information about the methods employed for this study.

G Data Handling and Record Keeping

G1 Confidentiality and Security

Every effort will be made to keep Personally Identifiable Information (PII) associated with the study confidential: (1) subjects will be assigned a code number and only the code number will be used to identify the limited clinical information that will be analyzed; (2) the computers on which the data will be stored are password protected and all of them are located in offices with key locks; (3) written documents concerning the study will be kept in locked cabinets; (4) all personnel involved in human subject testing will have completed the appropriate HIPAA training and be fully aware of the need for confidentiality regarding PII. No health information will be acquired for this study.

G2 Training

All study team members are required to take IRB compliance training. At a minimum, this consists in Basic Human Subjects Research (CITI) training, Health Privacy Issues for Researchers training, and Conflict of Interest and Commitment training per JHM IRB policy, in addition to Good Clinical Practice training as required by NIH. PIs are also required to take Research Ethics Workshops About Responsibilities and Duties of Scientists training.

G3 Records Retention

In accordance with IRB policy, records will be retained for five years after the date of the last publication associated with the study.

G4 Performance Monitoring

Data will be analyzed following each testing session to evaluate system performance.

H Study Monitoring, Auditing, and Inspecting

H1 Study Monitoring Plan

This is a non-significant risk study. The PIs at each site are responsible for the monitoring and execution of the testing. The JHM IRB, as the single IRB of record, will be responsible for reviewing the study protocols, consent forms, and case report forms.

H2 Auditing and Inspecting

This is a non-significant risk study. The JHM IRB regularly conducts audits to ensure that studies are in compliance.

I Study Administration

I1 Organization and Participating Centers

The following centers are involved in the study described in this protocol:

- Johns Hopkins University Applied Physics Laboratory, Laurel, MD
- Johns Hopkins Medicine, Wilmer Eye Institute, Baltimore, MD
- Johns Hopkins University Homewood Campus, Baltimore, MD
- Carnegie Mellon University, Pittsburgh, PA

I2 Funding Source and Conflicts of Interest

This research is supported by National Institutes of Health (NIH) National Eye Institute (NEI) grant number 1R01EY029741-01.

I3 Subject Stipends or Payments

Subjects recruited from the Applied Physics Lab will be paid for their time in accordance with APL policies. Subjects recruited from the JHU Homewood campus will be uncompensated. Argus II users will be reimbursed for their costs associated with the study, such as travel to the testing facility and lodging, and will be provided with meals throughout their participation in the study.

I4 Study Timetable

Testing will commence upon IRB approval of the study and continue through the duration of the grant, expected to end in July 2024. Requests for changes in research and extensions to the protocol will be made as necessary during this time.

J Publication Plan

Deidentified data and results from this study may be submitted for submission to peer-reviewed conferences and journals, as well as abstracts and presentations at sector specific conferences (e.g. NIH Brain Initiative meeting).

K Attachments

K1 Informed consent documents

Informed consent documents are attached.

L References

- [1] National Eye Institute, NIH, “Blindness.” [Online]. Available: <https://nei.nih.gov/eyedata/blind>.

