Figure 2 represents an example scenario where an Argus II user has requested guidance to the nearest door. The door has already been identified by object recognition during algorithm testing and stored in the system’s map of the environment. The path to the door is impeded by a couch, which is also stored in the map as an obstacle labeled by object recognition. Upon receiving the user request, the system computes a path around the couch to the door and initiates navigational cues to guide the user along the planned path. As the user progresses along this path, the door is enhanced (brightened) in artificial vision as being the target destination. Nearby obstacles (such as the couch) are also shown through the prosthesis (or the simulated prosthesis for normally sighted participants), while the system’s stereo-vision-based obstacle detection feature continually monitors the scene for both mapped and previously undetected obstacles along the way.

In addition to the navigation itself, participants will provide numerical ratings on scales to indicate the mental (cognitive) load of the task, perceived effort, and ease of travel. Participants will also provide qualitative answers to questions pertaining to their experience using the system, such as what elements of the system were more or less helpful and how they believe the system could be improved.

During the consent process, participants will be given the opportunity to consent to audio-video recordings being taken of them while performing the tasks of this study. Consenting to audio-video recording is not mandatory for subjects to participate in the study. For those participants who consent to audio-video recording, the recordings may be used to help analyze the participant’s performance in the study and may be used in presentations of the methods and outcomes of the study before a general audience. Audio-video recordings will not be used for advertising or non-study related purposes.

[figure not shown]

Figure 2 - Example navigation scenario for a blind user; although not shown in the figure, information communicated by the system to the user also enables the user to mentally form an egocentric spatial image of their surroundings.

D2 Subject Selection and Withdrawal

2.a Inclusion Criteria

Criteria for inclusion of normally sighted individuals:

- Subject speaks English;
- Subject is an adult (at least 18 years of age);

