Participants may also become *frustrated or disappointed* if they feel they are not performing well. We will remind participants that this technology is novel and has potential benefits for other Argus II users and others with very limited visual acuity. As mentioned above, we will ask participants whether they want to interrupt testing to discuss this in more detail or if they wish to withdraw altogether.

The research information obtained from human subjects will consist of eligibility data, user-specific configuration settings for the Argus II device, sensor data required to create maps of the testing environment, and behavioral data (includes video). As a result, there is a risk of *breach of confidentiality*. This is mitigated by ensuring that all PII is stored on password protected computers at all sites.

Risks for Argus II Users:

For Argus II users there are no risks associated with using the Argus II device that are greater than the risks that participants face using their Argus II device in their everyday lives. In accordance with the device's Safety and Probable benefit document (https://www.accessdata.fda.gov/cdrh_docs/pdf11/H110002B.pdf), the following precautions will be followed:

- In the event of any undesirable sensation when using the device, all operations will be halted, and Argus II glasses will be removed or the Argus II Visual Processing Unit (VPU) will be turned off.
- Argus II users will only use a VPU that has been specifically programmed for them by their clinician or Second Sight personnel.
- Argus II users will continue to use their other mobility aides, such as a cane, at all times.

Risks for JHU/APL Participants:

Normally sighted study participants at JHU/APL will be asked to don a head mounted display for extensive periods of time. In addition to the common risks mentioned above, there is a *risk of dizziness and fatigue* caused by extensive use of the HMD. As above, this risk is mitigated by taking as many breaks as

participants request as well as interrupting testing and potentially resuming on a different day if requested by a participant. Here too, participants are free to withdraw from the study at any time.

Benefits:

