Potential benefits that individual participants may experience from taking part in this research stems from the new sensory information afforded to prosthetic vision users by providing them with object recognition and navigational capabilities, as well as the addition of haptic and auditory sensory feedback to supplement prosthetic vision. This may help current and future prosthetic vision users to independently form mental maps of their surroundings using their prosthetic vision device and allow users to gain confidence in using the device for navigating new environments.

2.d Early Withdrawal of Subjects

In all cases, expected time commitments will be clearly communicated to participants ahead of time. It will also be clearly communicated to participants that they may choose to withdraw from the research at any time for any reason.

2.e When and How to Withdraw Subjects

Subjects will be withdrawn early from the study anytime upon subject request. It is also possible that other factors may contribute to the need for early withdrawal. For example, a malfunction of the system may cause us to have to stop testing. No special procedures are associated with withdrawing a subject early from this study other than to discontinue testing. Participants will be compensated for their time spent participating in the study prior to early withdrawal as described in Section I3.

2.f Data Collection and Follow-up for Withdrawn Subjects

In case of early withdrawal, no further data gathering nor follow-up will be conducted with the subjects. As for all subjects, if a subject consents to be contacted for future research, they may be contacted later for future studies.

D3 Study Device

3.a Description

The following devices are used in this study. No device will be used with any study participant prior to being reviewed and approved by Johns Hopkins' clinical engineering services (CES).

- Argus II Retinal Prosthesis System: used in this study by Argus II users who have a pre-existing implanted retinal prosthesis. This is an FDA approved device and will be used according to its intended use.

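### Withdrawal may be related to performance, but F1's conventional within-subject ANOVA and F2's sighted baseline make no provision for participants who leave early

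*Combined protocol and SAP*

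**What the plan says.** All sections are in the combined protocol and SAP.

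- **D2, 2.c Risks and Benefits (all participants).** Participants may become frustrated or disappointed "if they feel they are not performing well". The response has two parts: "We will remind participants that this technology is novel and has potential benefits for other Argus II users", and then "we will ask participants whether they want to interrupt testing to discuss this in more detail or if they wish to withdraw altogether".
- **D2, 2.d and 2.e.** Everyone is told that "they may choose to withdraw from the research at any time for any reason". Withdrawal can also have technical causes: "a malfunction of the system may cause us to have to stop testing".
- **D2, 2.f.** After early withdrawal, "no further data gathering nor follow-up will be conducted with the subjects". What happens to data already collected is not stated.
- **F1.** For sighted subjects, "we use within-subject factorial designs and test with conventional ANOVA statistics". F1 also describes each participant as supplying a full copy of the experiment.
- **F2.** On each measure, an Argus II user is placed by z-score against the sighted mean and variance.

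The document gives no expected dropout rate, missing-data rule, analysis set, replacement rule or order of systems, and does not plan to record reasons for withdrawal.

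**The concern.** 2.c puts the question about leaving to people who think they are doing badly, and 2.f stops their data at that point. If some accept, the missing conditions belong disproportionately to weaker performers.

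Two analyses are exposed, in different ways. A conventional repeated-measures ANOVA needs every condition from every subject and ordinarily drops those who lack one. The system contrast is then biased if leaving is related to the difference between systems, and leaving after a poor result on one system creates such a relation. The sighted baseline is exposed more simply. On measures taken after the departures, the mean and variance describe those who stayed, so the mean is too high and the SD too small. Argus II users then look further from baseline than they are. This matters because F1 rules out significance testing for them and relies on comparison with the sighted group.

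**Working it through.** **The plan's own figure.** F1 gives 20-30 sighted subjects for power above 0.80 at the 0.05 level. This cannot be reproduced, because no effect size, SD or within-subject correlation is printed. Solving backwards with a two-sided paired t-test, 80% power needs a standardised difference of 0.66 at n = 20 or 0.53 at n = 30. The range is plausible but cannot be checked.

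**Assumed inputs (none is in the document).** Scores are normal with SD 1, higher is better. A fraction d withdraws, being the lowest scorers on the system tested first. The correlation is ρ = 0.5 between systems and between measures. The true gain is 0.50 SD.

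**Mean of those who stay.** With c the d-quantile of the standard normal, the stayers' mean on the first system rises by λ = φ(c)/(1 − d), and on the second system by ρλ.

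**System contrast, completers only, Basic first for everyone.** Estimated gain = 0.50 − (1 − ρ)λ.

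| d | λ | Estimated gain |
|---|---|---|
| 10% | 0.195 | 0.50 − 0.5 × 0.195 = 0.40 |
| 15% | 0.274 | 0.50 − 0.5 × 0.274 = 0.36 |
| 20% | 0.350 | 0.50 − 0.5 × 0.350 = 0.325, or 0.33 |

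How far this depends on the assumptions:
- With ρ = 0.7 and d = 15%: 0.50 − 0.3 × 0.274 = 0.42.
- If felt performance correlates only 0.5 with the score, the bias halves. At d = 10%: 0.50 − 0.5 × 0.5 × 0.195 = 0.45.
- If the augmented system comes first for everyone, the sign reverses. At d = 10%: 0.50 + 0.5 × 0.195 = 0.60.
- If order is counterbalanced and the same fraction leaves in each order, the two biases cancel and the estimate is 0.50.

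**Effect on the test.** With equal variances, the correlation of the first score with the difference (second minus first) is −√((1 − ρ)/2) = −0.5. Simulation of a null contrast at that strength (20,000 runs, 30 enrolled, completers only) gives a type I error of 0.08 at 10% dropout and 0.14 at 20%. It stays near 0.05 when dropout is unrelated to the contrast.

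**Sighted baseline on a later measure.** Stayers' mean = ρλ, SD = √(1 − ρ²λ(λ − c)), and the reported z = (true z − mean)/SD. For a true z of −1.5:

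| d | Mean | SD | Reported z |
|---|---|---|---|
| 10% | 0.0975 | √(1 − 0.25 × 0.288) = 0.963 | −1.66 |
| 15% | 0.137 | √(1 − 0.25 × 0.359) = 0.954 | −1.72 |
| 20% | 0.175 | √(1 − 0.25 × 0.417) = 0.946 | −1.77 |

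**Likelihood-based estimate.** Using the leavers' completed scores, the maximum-likelihood estimate returns 0.50 in each simulated case. This holds by construction, because dropout there depends only on a score that was observed.

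**The case against.** The strongest reply is that much of this is inferred. The trigger in 2.c is a feeling, with no performance threshold. A pause to talk is offered beside withdrawal, the reminder favours staying, and everyone may leave at any time. The net effect on dropout is unknown. F1 names no completers-only set, and 2.f stops further collection without discarding what exists. The z-score is also not the only yardstick. E6 assesses each Argus II user individually for lower error under augmentation, and F2 adds fixed literature standards and device-pixel error. None of these needs the sighted mean and variance. All of this stands, and it limits both the certainty and the size of the point.

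It does not close the gap. Conventional repeated-measures ANOVA ordinarily excludes incomplete subjects, and F1's picture of every participant completing everything fails for anyone who leaves.

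A reader might also infer that the reminder of benefits contaminates the workload, effort and ease-of-travel ratings described in D1. The document does not time the reminder relative to those ratings, and the reminder concerns possible benefit to others, so that is not supported. Nor is there a case for rewriting 2.c: a scripted check-in at fixed times would leave people equally free to quit when doing badly, and would replace a welfare step with a preference.

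**Conclusion.** The point holds as a risk that the analysis plan leaves open. Dropout may be related to performance, the planned ANOVA would ordinarily drop those who leave, and later baselines would rest on those who stay.

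Under strict worst-first loss of 10-20%, one system order for all and a correlation of 0.5, a gain of 0.50 SD is estimated as 0.40 to 0.33. That is about 19-35% of the effect. It is close to a worst case: the bias shrinks with a weaker trigger, vanishes under balanced order and reverses if the augmented system comes first. For later measures, a z of −1.5 moves by about 0.16 at 10% dropout and 0.22 at 15%.

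Two stronger readings are tempting and unsupported. One is that the protocol makes dropout depend on performance; it only makes that possible. The other is that a z of −1.5 would be reported as −2.0 (10% dropout) or −2.2 (15%). Those values apply to the measure that prompted the withdrawal, and only if scores already collected on it are thrown away, which no section says.

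**What to change.** Change F1 and F2 only:

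1. State that all trials completed before withdrawal are kept.
2. Analyse the sighted data with a likelihood-based mixed model on all available trials, in place of the conventional ANOVA with its usual exclusion of incomplete subjects.
3. Include leavers' completed data in the mean and variance behind each z-score.
4. Report withdrawals by reason and by system in use.
5. As a sensitivity analysis, report z-scores with and without leavers. This is needed because the mixed model covers only dropout explained by observed performance, whereas the trigger is how participants feel. The comparison is informative only for measures on which leavers supplied trials; for measures they never reached, the text should say so.

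Leave the 2.c welfare wording and the freedom to withdraw as they are. The cost is a few lines in F1/F2 and slightly more modelling work, with no extra participants or staff.

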Testing is expected to be conducted over a 1-5 day period for each participant. We anticipate that testing will require less time for the normally sighted participants than for the Argus II users.

E3 Visit 1

Apart from the consent process that occurs at the beginning of the first visit, the testing performed during the study visits will be similar to each other. For the consent process, the PI or authorized study team member will guide interested subjects through the informed consent form. Following consent, participants will be asked to perform three groups of tasks, as described in Section D1. Participants will be informed during consent that while breaks will be provided during the course of testing, they are also free to interrupt testing at any time to take breaks.

E4 Following Visits

See Section E3.

E5 Safety and Adverse Events

Study team members will complete all IRB training required to conduct the experiments described in this application prior to being involved in any human subject testing.

Communication between sites is primarily facilitated via working conference meetings held at least once per month between key team members from each site. Planning for significant protocol events regarding the study, such as amendments to study protocols, annual approvals, etc., will be discussed among all sites in these meetings, as well as communicated between sites via email where appropriate. A Box share folder has also been set up to host and distribute information among all sites and will serve as a single point of reference for obtaining the most up-to-date information regarding the study, such as the most current version of the study protocol.

Both the PI ([name]) and the site-PI's at each study location will be responsible for monitoring participant safety, evaluating the progress of the study, reviewing procedures for maintaining the confidentiality of data, the quality of data collection, management, and analyses, in accordance with guidance provided by the IRB of record. In case of protocol events or deviations at participating sites, any team member aware of the issue will promptly notify the PI ([name]) and site-PI, and a report will be promptly submitted to the IRB (and sponsoring agency if appropriate) per the JHM IRB's prompt reporting requirements, as described further below.

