The research data will be reviewed every day that data are collected, and the accrued data reviewed again at the end of the study to ensure its validity and integrity. The PI will conduct study team meetings on at least a monthly basis to discuss study progress, data quality and any unanticipated problems or findings will be reported upon occurrence. Reports concerning the progress of the study and subject status will be provided in the study closure report or when requested by the IRB.

If any protocol changes are needed, they will not be implemented prior to IRB approval, with possible exception of minor or administrative deviations which do not affect the scientific soundness of the research plan or the rights, safety, or welfare of human subjects. If a protocol deviation occurs which meets this definition for a minor deviation, the deviation will be reported to the JHM IRB at the time the continuing review application is submitted in eIRB using the Protocol Deviation Summary Sheet (R.F. 4).

In the event of an emergency protocol deviation taken without prior IRB approval to protect the life or physical well-being of a participant, it will be reported to the sponsor and the IRB of record as soon as possible, but not later than 5 days after the emergency situation occurred.

The research teams at all site locations will monitor subjects for adverse events throughout the study. Adverse events that fit the following criteria will be reported to JHM IRB within 10 working days from the time when the principal investigators become aware of them per JHM IRB policy:

- Event is UNEXPECTED (in terms of nature, severity, or frequency) given (a) the research procedures that are described in the protocol-related documents, such as the IRB-approved research protocol and informed consent document, and (b) the characteristics of the subject population being studied;
- RELATED or POSSIBLY RELATED to participation in the study (possibly related means there is a reasonable possibility that the incident, experience, or outcome may have been caused by the procedures involved in the study); and

- Suggests that the study PLACES SUBJECTS OR OTHERS AT A GREATER RISK OF HARM (including physical, psychological, economic, or social harm) than was previously known or recognized.

The following unanticipated problems that are not adverse events will also be reported to the IRB within 10 days of becoming aware of them:

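### Section 2.f rules out all follow-up after early withdrawal and makes no exception for an unresolved study-related adverse event

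*Combined protocol and SAP*

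**What the plan says.** Section D2, 2.f sets the rule for participants who leave early: "In case of early withdrawal, no further data gathering nor follow-up will be conducted with the subjects". The only later contact it mentions is for recruitment: "As for all subjects, if a subject consents to be contacted for future research, they may be contacted later for future studies". Section 2.e adds that withdrawal involves no particular procedure beyond stopping the testing.

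Adverse events are handled in E5. On monitoring it says: "The research teams at all site locations will monitor subjects for adverse events throughout the study". Events that are unexpected, at least possibly related, and suggestive of greater risk than was known "will be reported to JHM IRB within 10 working days from the time when the principal investigators become aware of them". E5 also makes the principal investigator and the site investigators responsible for participant safety. Section 5.f (reporting period) only refers back to E5. Section 5.g says: "This is a non-significant risk study, no post-study adverse events are anticipated".

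**The concern.** The protocol names the kinds of event that could make someone stop. Section 2.c lists tripping or stumbling, fatigue, headache and backache for all participants, and dizziness from long headset use for sighted participants. For Argus II users it foresees an undesirable sensation, to be met by halting and then removing the glasses or switching off the processing unit. A participant who stops for one of these reasons falls under 2.f, which ends follow-up along with data gathering.

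What is at stake is the welfare of that participant. Staff who apply 2.f as written would not contact the person to ask whether the problem had settled. They could also miss a worsening that bears on whether the event must be reported.

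**Working it through.** The plan gives no figure on this point, so the check sets the relevant sections side by side.

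1. **Is 2.f a rule or a silence?** It is a rule. It ends two things, data gathering and follow-up, and carries no safety exception. The future-studies contact is for another purpose and depends on separate consent.

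2. **Does the withdrawal procedure fill the gap?** No. Under 2.e the only step is to stop testing. No safety check at exit is stated.

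3. **Does the schedule fill it?** No. E2 says: "Testing is expected to be conducted over a 1-5 day period for each participant". Section 2.c lets testing be interrupted and resumed on a different day, so the calendar span can vary. No contact after the last session is scheduled, and someone who has withdrawn has no further session.

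4. **Does E5 fill it?** In part. It assigns responsibility for safety, requires monitoring, and starts the reporting clock at awareness with no cut-off at withdrawal. A problem that a former participant volunteers later can therefore still be reported. E5 does not say that an event will be followed until it resolves or stabilises. Its reporting criteria also require the event to be unexpected in nature, severity or frequency. Trips and dizziness are foreseen in nature, so they would mostly qualify through unexpected severity or frequency. How long an event lasts can inform a judgement of severity, and 2.f, read literally, blocks the question.

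5. **Do the other safety sections fill it?** No. Section 5.g states an expectation and gives no procedure. Medical monitoring (5.a) is marked not applicable, and 2.c rules out exchanging information with physicians, so no clinical route to the outcome is described.

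6. **To whom could 2.f apply?** To any participant, since all may withdraw. D1 lists three sets: 5 + 25 + 10 = 40 at the low end and 15 + 35 + 10 = 60 at the high end. B2 lists only sighted adults and prosthesis users: 25 + 5 = 30 to 35 + 15 = 50. These totals are the people covered by the rule, not the number expected to need follow-up. The documents give no withdrawal rate and no rate of unresolved events, so that number cannot be derived.

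**The case against.** The strongest reply is that 2.f is about research follow-up. It sits under subject selection and withdrawal and respects the right to stop at any time for any reason. Adverse events belong to E5, which does not exclude people who have withdrawn. On that reading a safety call was never forbidden. This is a fair reading, and it is why the point says only that 2.f blocks follow-up if taken literally. But the text does not make the distinction, and a site applying the specific sentence in 2.f could reasonably conclude that no call should be made.

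The second reply is proportionality. There are no medical procedures, participants walk slowly or stand, staff stay close, and the team reports that its tripping risk has never materialised. For implant users the stated risk is no more than that of everyday use. All of this stands and keeps the point small. The reassuring record covers tripping only, however, and low risk makes follow-up rare without being a reason to rule it out.

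Third, the consent documents, which K1 says are attached, are not in the text reviewed and may contain injury or contact instructions. The point therefore concerns protocol wording only.

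Stronger readings are tempting, but the documents do not support them:

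- A reader might infer that nobody is responsible for such a participant. E5 gives that responsibility to the principal investigator and site investigators.
- A reader might infer that completers are equally cut off. Sections E5, 5.f and 5.g state no follow-up rule for them, but nothing there bars follow-up. For completers this is unwritten detail.
- A reader might infer from G1, "No health information will be acquired for this study", that following an event would also breach the confidentiality section. E5 already requires adverse events to be monitored and reported without any exception in G1, and G1 itself refers to limited clinical information being analysed.

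**Conclusion.** The point holds for participants who withdraw early. Section 2.f excludes follow-up in words, makes no exception for an adverse event that is ongoing at, or led to, withdrawal, and no other section reviewed supplies one. The conclusion rests on reading 2.f literally and on the protocol text alone.

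Its size is modest. It is a matter of participant safety in a non-significant-risk study, softened by the assigned responsibility for safety and by reporting that runs from awareness. A reader might infer some bias in the results. The documents give no ground for that: the Statistical Plan analyses task performance, and the proposed clause leaves performance data collection after withdrawal as it is, namely stopped. No estimate of how many people would be affected is offered, because the documents give no event rate.

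**What to change.** Replace the follow-up sentence in 2.f with wording such as: *After early withdrawal no more performance data will be collected. Any study-related adverse event or undesirable sensation that is ongoing at, or led to, withdrawal will be followed, with the participant's agreement, by phone or email until resolved or stable.* Optionally, add a cross-reference in 5.g so that the same step applies to an event still open at a completer's last session. G1 need not change.

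The cost is one protocol amendment. E5 says: "If any protocol changes are needed, they will not be implemented prior to IRB approval", so approval must come first; I4 already expects requests for changes during the study. In practice it adds a rare call or email to an affected participant who agrees, and nothing for anyone else. The agreement condition preserves the right to leave without further contact.
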